#### Efficacy Analysis

In addition to the PK modelling, the primary endpoint may be analysed including data from all available cohorts, after the final visit of the last subject from the second consecutive cohort that reaches or exceeds the target PK plasma exposure for efficacy. The purpose of this efficacy analysis is to optimise dosing for subsequent cohorts (e.g. to help estimate the dose response curve) as well as to aid internal decision making. If this cohort is the fifth (final) cohort then the efficacy analysis will be performed as part of the final SAC deliverable. The primary endpoint will be analysed as planned for the final analysis, see Section 7: Efficacy Analyses.

The efficacy analyses will be performed after the completion of the following sequential steps:

1. All participants in the current cohort have completed their Day 15 study visit as defined in the protocol.
2. Data have been made available by Data Management (no specific data cleaning requirements for the efficacy analysis).
3. All criteria for unblinding the randomization codes have been met.
4. Randomization codes have been distributed according to RandAll NG procedures.

### 3.2. Final Analyses

The final planned primary analyses will be performed after the completion of the following sequential steps:

1. All participants have completed the study as defined in the protocol.
2. All required database cleaning activities have been completed and final database release (DBR) and database freeze (DBF) has been declared by Data Management.
3. All criteria for unblinding the randomization codes have been met.
4. Randomization codes have been distributed according to RandAll NG procedures.

## 4. ANALYSIS POPULATIONS

Population	Definition / Criteria	Analyses Evaluated
Screened	
 
• All participants who were screened for eligibility
 
	
 
• Study Population
 

Randomized	
 
• All participants who were randomly assigned to treatment in the study.
 
• This population will be based on the treatment the participant was randomized to.
 
• Any participant who receives a treatment randomization number will be considered to have been randomized.
 
	
 
• Study Population
 

Enrolled	
 
• All participants who passed screening and entered the study. Included are run-in failures and randomized participants.
 
• Note: screening failures (who never passed screening even if rescreened) and participants screened but never enrolled into the study (Reserve, Not Used) are excluded from the Enrolled population as they did not enter the study.
 
	
 
• Study Population
 

Safety	
 
• All randomized participants who received at least one dose of study treatment.
 
	
 
• Safety
 

Population	Definition / Criteria	Analyses Evaluated
	
 
• Participants will be analysed according to the treatment they actually received.
 
• Note: Participants who were not randomized but received at least one dose of study treatment should be listed.
 
	
Efficacy	
 
• All participants in the safety population who provided at least two evaluable overnight sputum samples.
 
• This population will be based on the treatment the participant was randomized to.
 
	
 
• Efficacy
 

Pharmacokinetic (PK)	
 
• Participants in the safety population who received at least one dose of GSK3036656 and have at least one evaluable PK sample.
 
• Participants will be analysed according to the treatment actually received.
 
	
 
• PK
 

For participants who receive the incorrect treatment (i.e. a different treatment to what they were randomised to), the participants will be assigned to the actual treatment groups if they received that treatment for more than 50% of their doses.

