## 8. DISCONTINUATION CRITERIA

If study treatment/investigational product is interrupted or stopped this does not automatically result in the participant being withdrawn from the study. The investigator will make all effort to retain the patient in the study, provided the participant continues to provide their consent, and to complete and record all scheduled safety assessments required by the protocol. For the avoidance of all doubt: this does not prejudice the rights of the investigator and study participants under ICH GCP and under applicable laws. The study participant retains the right to withdraw consent at any time for any reason. The investigator also retains the right to withdraw the patients from the study if in the investigator's judgement, withdrawal is judged clinically necessary to protect a participant's safety.

If this results in the patient being placed on standard of care (i.e. Rifafour e-275 or equivalent generic alternative), then all assessments relevant to Rifafour e-275 (or equivalent generic alternative) will be performed as directed by the protocol (for

example, GSK3036656 pharmacokinetic assessments are not required, since the participant is not being dosed with GSK3036656).

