### 2.3. Study Design

Overview of Study Design and Key Features	
<pre> graph LR     A[SCREENING from -9 days prior to first dose] --> B[14-Day treatment period - GSK3036656]     A --> C[14-Day treatment period - Rifafour]     B --> D[Day 15 start/continue Rifafour*]     C --> D     D --> E[Follow-up at Day 28]             </pre> 
*This is not part of the study but is the post-study definitive treatment of TB.
	
Design Features	
 
• A single-centre, open-label trial in up to five sequential cohorts.
 
• Each cohort will involve participants being randomised to one of two possible treatments: either GSK3036656 or Standard-of-Care (SoC) regimen (e.g. Rifafour®e-275) for rifampicin-susceptible (drug sensitive) tuberculosis (DS-TB).
 
• Screening will be performed on days -9 to -1, followed by 14 days of once daily dosing and a follow-up visit 28 days after the first dose.
 
• All laboratory staff involved in analysing and reporting the primary and secondary change in CFU counts and TTP endpoint results will be blinded to treatment allocation.
 

Dosing	
 
• Once daily repeat dosing for 14 days.
 
• The starting dose for the GSK3036656 arm is a 15mg loading dose on Day 1 and 5mg maintenance dose on Days 2-14, given orally. The study will employ dose escalation, where the GSK3036656 dose for each cohort will be decided based on reviews of preliminary safety, tolerability and pharmacokinetic data; in addition, efficacy data will be considered if available.
 

Time & Events	
 
• See Appendix 2: Schedule of Activities
 

Treatment Assignment	
 
• 12-20 participants in each cohort (excluding possible replacements), randomised 3:1 to GSK3036656 or Standard of Care respectively.
 
• GSK RandAll NG will be used to generate the randomisation schedule.
 

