#### **7.1.4. Strategy for Intercurrent (Post-Randomization) Events**

The primary treatment effect to be estimated will be the while on treatment effect of initial randomised treatment.

All recorded data up to the time of study withdrawal will be included in the analysis, regardless of discontinuation of study medication.

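### The more-than-50%-of-doses rule in SAP Section 4 has no exemption for the protocol's own move to standard of care, so an early GSK3036656 stopper could be tabulated under Rifafour in the safety tables

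*SAP*

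**What the plan says.** The table in SAP Section 4 sets a grouping basis for each population. Safety and PK go by the treatment actually received. For efficacy the table says "This population will be based on the treatment the participant was randomized to", and SAP 7.1.4 agrees: "The primary treatment effect to be estimated will be the while on treatment effect of initial randomised treatment".

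A free-standing paragraph after the table deals with mixed dosing. It opens "For participants who receive the incorrect treatment (i.e. a different treatment to what they were randomised to" and continues "the participants will be assigned to the actual treatment groups if they received that treatment for more than 50% of their doses". It is not tied to a population and lists no exceptions.

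Protocol Section 8 says: "If study treatment/investigational product is interrupted or stopped this does not automatically result in the participant being withdrawn from the study". The next paragraph, opening "If this results in the patient being placed on standard of care", goes on to say that the assessments relevant to Rifafour are then carried out under the protocol, without GSK3036656 pharmacokinetics. An in-study move from GSK3036656 to Rifafour is therefore foreseen.

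**The concern.** The SAP's own gloss on incorrect treatment is any treatment other than the randomised one. A participant moved to Rifafour under Protocol Section 8 fits that gloss, although nobody made an error. If Rifafour then supplies more than half of the doses, the rule places the participant in the Rifafour group for populations grouped by treatment received.

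Those who could be moved this way are the ones who stopped GSK3036656 earliest, and a safety stop is one reason for that. Protocol Appendix 7 (liver) requires study treatment to be discontinued but keeps the participant in the study for follow-up, and the Schedule of Activities places safety bloods within Days 2 to 7. The event that ended GSK3036656 treatment would leave the dose group that produced it and be counted under the benchmark regimen. Along this route the shift always runs in that direction.

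Nothing later in the SAP corrects this. The treatment-emergent flag in SAP 12.4.2 sets a time window and does not attribute an event to the treatment being taken at onset. Safety and tolerability is a secondary objective, and later GSK3036656 arms may have only 9 participants (Protocol 10.1.2). In the PK population the same rule could place a GSK3036656 participant who has a usable sample in a group with no GSK3036656 dose.

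**Working it through.** The plan gives no figure on this point, so there is nothing to reproduce. The check is a dose count.

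**Inputs**
- Planned doses: 14, from SAP 2.3 ("Once daily repeat dosing for 14 days").
- Threshold: strictly more than 50% (SAP Section 4).
- GSK3036656 arm size: 9 in ongoing and future cohorts (Protocol 10.1.2); 15 in the initial plan (Protocol 10.1.1).
- Standard of care: pooled for the final analysis (Protocol 10.2) and shown as a single Rifafour group (SAP 5.1).
- Assumptions: Rifafour after the stop counts as dosing, is counted as one dose per day, and runs to Day 14.

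**Share of doses that are Rifafour.** Let k be the number of GSK3036656 doses taken and g the number of days without a dose before Rifafour starts. Then share = (14 − k − g) / (14 − g), and the participant changes group if share > 0.50.

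| Gap g | Last k that is reassigned | Next k |
|---|---|---|
| 0 days | k = 6: 8/14 = 57.1% | k = 7: 7/14 = 50.0%, stays |
| 1 day | k = 6: 7/13 = 53.8% | k = 7: 6/13 = 46.2%, stays |
| 2 days | k = 5: 7/12 = 58.3% | k = 6: 6/12 = 50.0%, stays |
| 3 days | k = 5: 6/11 = 54.5% | k = 6: 5/11 = 45.5%, stays |

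So the boundary is the first 6 doses with a gap of at most one day, and the first 5 doses with a gap of two or three days.

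**Effect of one case on the tables**
- GSK3036656 arm of 9: 1/9 = 11.1% becomes 0/8 = 0%.
- GSK3036656 arm of 15: 1/15 = 6.7% becomes 0/14 = 0%.
- Pooled Rifafour: the final pool size is not known. Assuming 13 participants (three cohorts of 5 + 5 + 3), 19 (5 + 5 + 3 + 3 + 3) or 25 (five cohorts of 5), and no such event otherwise, the entry becomes 1/14 = 7.1%, 1/20 = 5.0% or 1/26 = 3.8%.

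**Who is outside the route.** Participants withdrawn from the study are not affected, since any later Rifafour is off-study. The QTc criteria in Protocol 8.1.2 lead to withdrawal. For haemoglobin and neutrophil stops, Protocol 3.3.1 speaks of withdrawal from the study while Protocol 8.1.3 speaks only of discontinuing the product. Those two sections need reconciling before one can say whether such stops fall under the rule.

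**The case against.** The strongest reply is that the rule was written for dosing errors. Its first words limit it to incorrect treatment, and a move that the protocol permits is not incorrect. This is a natural reading and may well be what was meant. But the SAP then defines the term by a gloss that a switch satisfies, and a programmer would work from that gloss.

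Second, it is not settled that Rifafour after a stop belongs in the dose count. The SAP generally treats discontinuation as the end of study treatment: the on-treatment period closes 48 hours after the stop (SAP 12.4.1) and exposure runs to the stop date (SAP 12.6.2). On the other side, Protocol Section 7 defines study treatment broadly enough to include a marketed product given under the protocol, and Section 7.1 lists Rifafour as one. The point stays open, so the conclusion has to be conditional on it.

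Third, the route is narrow. It needs an early stop, continued participation, an in-study switch and little delay. Safety is summarised descriptively, no formal comparison with standard of care is planned, and listings of planned and actual treatment, exposure and adverse events (SAP 12.10.11) would let a careful reader trace a case. All of that stands. It limits the consequence, but it does not correct the summary tables.

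Three stronger readings are tempting and are not supported:
- **That two analysts could reach different primary results.** The efficacy row of SAP Section 4 and SAP 7.1.4 both fix efficacy to randomised treatment. A general sentence should not override two specific ones.
- **That a 9:3 cohort would show standard of care going from 0/3 to 1/4.** Standard of care is pooled in the final analysis, so that is not a planned safety column.
- **That dose escalation would be misled.** The safety tables in SAP 12.10.7 are produced for the final report only, and the documents do not show that the committee's safety review uses these groupings.

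**Conclusion.** The point holds as a gap in wording with a possible consequence for the final safety tables. As written, the rule allows a participant who stopped GSK3036656 early, and the event behind the stop, to be reported under pooled Rifafour.

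This depends on three conditions: the SAP's gloss is applied literally, Rifafour after the stop is counted as dosing, and the participant stays in the study and switches within the limits worked out above. Under those conditions one case removes 11 percentage points from a 9-participant arm. The documents give no number of switchers, so a bias is possible but not demonstrated, and the effect is zero if nobody switches. It is a modest point, worth acting on because the remedy costs very little.

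**What to change.** Reword the paragraph after the population table in SAP Section 4 along these lines: *The rule on more than half of doses applies to the safety and PK populations only, and only to dispensing or administration errors. Efficacy is analysed by randomised treatment. A participant randomised to and dosed with GSK3036656 who moves to standard of care under Protocol Section 8 stays in that GSK3036656 dose group; adverse events that start after the move are flagged in the listing.*

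The last provision should be limited to participants randomised to GSK3036656. A statement covering anyone who took a dose of it would clash with the error rule for a standard-of-care participant given one GSK3036656 dose by mistake.

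The cost is SAP wording and one flag in the adverse event listing. No new data are needed and no clinical rule changes. There is a small downside: events that arise on Rifafour after the switch are counted under GSK3036656 in the summary tables, and the flag is what lets a reader separate them.

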#### 4.1. Protocol Deviations

Important protocol deviations (including deviations related to study inclusion/exclusion criteria, conduct of the trial, patient management or patient assessment) will be summarised and listed.

Protocol deviations will be tracked by the study team throughout the conduct of the study in accordance with the latest Protocol Deviation Management Plan (PDMP).

- Data will be reviewed prior to freezing the database to ensure all important deviations and deviations which may lead to exclusion from the analysis are captured and categorised on the protocol deviations dataset.
- This dataset will be the basis for the summaries and listings of protocol deviations.

A separate summary and listing of all inclusion/exclusion criteria deviations will also be provided. This summary will be based on data as recorded on the inclusion/exclusion page of the electronic case report form (eCRF).

## 5. CONSIDERATIONS FOR DATA ANALYSES AND DATA HANDLING CONVENTIONS

### 5.1. Study Treatment & Sub-group Display Descriptors

Treatment Group Descriptions			
RandAll NG		Data Displays for Reporting	
Code	Description	Description 	Order in Tables, Figures and Listings
SOC	Standard of Care (Rifafour)	Rifafour	1
D1	GSK3036656 Dose 1	GSK3036656 5 mg	2
D2	GSK3036656 Dose 2	GSK3036656 15 mg	3
D3	GSK3036656 Dose 3	GSK3036656 30 mg	4
D4	GSK3036656 Dose 4	GSK3036656 X mg	5
D5	GSK3036656 Dose 5	GSK3036656 X mg	6

Note:

- The decision to proceed to each subsequent dose level will be made by the dose escalation committee.
- In tables, figures and listings, treatments should be presented with standard of care (Rifafour) first, then in order of increasing dose.
- [1] 'X mg' is to be replaced by actual maintenance dose.

### 5.2. Baseline Definitions

For all endpoints, except those noted below, the baseline value will be the latest pre-dose assessment with a non-missing value, including those from unscheduled visits (e.g. if Day 1 (pre-dose) is missing, Day -1 will be used). If there are no pre-dose data, then no derivation will be performed, and baseline will be set to missing.

For bacterial endpoints, baseline will be calculated as the mean of Day -2 and Day -1; if data are available at only one of these timepoints then that value will be used as baseline (i.e. data prior to Day -2 will not be used for calculation of baseline, even in the event there is missing data for both Day -2 and Day -1).

Unless otherwise stated, the mean of replicate assessments at any given time point will be used as the value for that timepoint.

If time is missing, Day 1 assessments are assumed to be taken prior to first dose and used as baseline.

### 5.3. Examination of Covariates

For the analysis of CFU and TTP, the demographic variable of Body Mass Index (BMI) will be included as a covariate in the model, see Section 7: Efficacy Analyses for further details.

Additional covariates of age (continuous), creatinine clearance (continuous), HIV status (yes/no), diabetes status (yes/no), smoking status (<20 or >=20/day) and baseline cavities (yes/no) will be investigated in an exploratory manner to assess their importance in future possible analyses.

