Section 11 Dose Escalation	
Changed from: "PK data in at least 10 subjects receiving GSK3036656 and selected safety data from all subjects in a cohort."
 
To: "PK data in at least 7 subjects receiving GSK3036656 and selected safety data from all subjects in a cohort"
	Based on the PK variability observed in the first two Cohorts, a sample size of 7 will give at least 80% power in the derivation of key PK parameters with an acceptable precision.
Section 11 Dose Escalation	
Changed from: "The primary endpoint may be analysed for all available cohorts after the final visit of the last subject on the second consecutive cohort that reaches or exceeds the target PK plasma exposure for efficacy (based on the murine infection model), and subsequent cohorts."
 
To: "The primary endpoint may be analysed once data is available for 12 evaluable subjects, as per the sample size re-estimation calculations, on the second consecutive cohort that reaches or exceeds the target PK plasma exposure for efficacy (based on the murine infection model), and subsequent cohorts."
	Updated to reflect changes in number of participants due to sample size re-calculations

Section #	Description of Change	Brief Rationale
Section 11 Dose Escalation	The following text was added: "To adjust the haemoglobin exclusion and stopping criteria if no haematological abnormalities are observed in the review of safety data from the highest dose cohort (Cohort 3). For the subsequent cohort(s) receiving a lower dose of GSK3036656, the haemoglobin exclusion criterion will be lowered to <8.0g/dL, and the haemoglobin stopping criterion will be lowered to <6.0g/dL. Patients with a confirmed haemoglobin <8.0g/dL after randomisation will require enhanced observations, with a repeat haemoglobin level and discussion of patient status with the GSK medical monitor."	A high number of screen fails have occurred due to haemoglobin levels being slightly lower than the current exclusion criteria (<10.0 g/dL), which is a common characteristic in this study population.

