## 6.2. Exclusion Criteria

Participants are excluded from the study if any of the following criteria apply:

1. Evidence of a clinically significant (as judged by the Investigator) condition or abnormality (other than the indication being studied) that might compromise safety or the interpretation of trial efficacy or safety endpoints.
2. Poor general condition where any delay in treatment cannot be tolerated per discretion of the Investigator.
3. Clinically significant evidence of extrathoracic TB (miliary TB, abdominal TB, urogenital TB, osteoarthritic TB, TB meningitis), as judged by the Investigator.
4. QTcF > 450 msec.
5. History of allergy to any of the trial IP/s or related substances as confirmed by the clinical judgement of the Investigator.
6. Participants with vitiligo.
7. Current alcohol or drug abuse, that is, in the opinion of the Investigator, sufficient to compromise the safety or cooperation of the participant.
8. HIV infected participants:
  - a. having a CD4+ count <350 cells/ $\mu$ L;
  - b. or having received antiretroviral therapy medication within the last 30 days;
  - c. or having received oral or intravenous antifungal medication within the last 30 days;
  - d. or with an AIDS-defining opportunistic infection or malignancies [CDC, 1993] in the last 12 months (except pulmonary TB).
9. Participated in other clinical studies with investigational agents within 8 weeks prior to the first dosing day in the current study.
10. Participants with diabetes (Type 1 or 2), point of care HbA1c above 6.5 %, or random glucose over 11.1 mmol/L will be excluded from cohorts undergoing CCI

11. Treatment received with any drug active against Mtb (including but not limited to isoniazid, ethambutol, fluoroquinolones, rifampicin), or with immunosuppressive medications such as TNF-alpha inhibitors or systemic or inhaled corticosteroids (used for > 5 consecutive days), within 2 weeks prior to screening. Refer to the SRM for details.
12. Unavoidable treatment with prohibited concomitant medications (see SRM)
13. Participants with the following abnormal laboratory values at screening as graded by the enhanced Common Terminology Criteria for Adverse Events (CTCAE v 5 2017):
  - a. haemoglobin <10.0 g/dL; this criterion may be adjusted following DEC review (see Section 11).
  - b. thrombocytopenia grade 2 or greater (under  $50 \times 10^9$  cells/L);
  - c. serum potassium grade 2 or greater (<3.0 mEq/L);

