## 10.3. Statistical Analyses

### 10.3.1. Activity/Pharmacokinetic Analyses

Endpoint	Statistical Analysis Methods
Primary	Rate of change in log 10 CFU per mL direct respiratory sputum samples over the period baseline to Day 14 (EBA CFU 0-14 ). This will be analysed using a mixed effects model including treatment, day, BMI and treatment-by-day as covariates.  This endpoint will be analysed using the efficacy population.
Secondary	PK Endpoints  Pharmacokinetic analysis will be the responsibility of the Clinical Pharmacology Modeling and Simulation Department, (CPMS), GlaxoSmithKline. Plasma GSK3036656 concentration-time data will be analyzed by non-compartmental methods with WinNonlin 5.2 or higher.

Endpoint	Statistical Analysis Methods

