The primary endpoint may be analysed once data is available for 12 evaluable subjects, as per the sample size re-estimation calculations, on the second consecutive cohort that reaches or exceeds the target PK plasma exposure for efficacy (based on the murine infection model), and subsequent cohorts. The purpose of this efficacy analysis is to optimise dosing for subsequent cohorts (e.g. to help estimate the dose response curve) as well as to aid internal decision making.

The DEC is empowered to take the following decisions for subsequent cohorts:

- To select a higher dose (including a loading dose that may be given over 1 or more days) within the limits defined in Section 5.6.
- To select a dose lower than, or the same as, a preceding dose.
- To stop dosing.
- To include additional pharmacokinetic assessments.
- To include additional timepoints for an existing safety assessment.
- To adjust the haemoglobin exclusion and stopping criteria if no haematological abnormalities are observed in the review of safety data from the highest dose cohort (Cohort 3). For the subsequent cohort(s) receiving a lower dose of GSK3036656, the haemoglobin exclusion criterion will be lowered to <8.0 g/dL, and the haemoglobin stopping criterion will be lowered to <6.0 g/dL. Patients with a confirmed haemoglobin <8.0g/dL after randomisation will require enhanced observations, with a repeat haemoglobin level and discussion of patient status with the GSK medical monitor.

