## 1. INTRODUCTION

The purpose of this reporting and analysis plan (RAP) is to describe the analyses to be included in the Clinical Study Report for Protocol:

Protocol Revision Chronology:		
2017N332005_00	09-FEB-2018	Original
2017N332005_01	20-FEB-2018	Protocol Amendment 1: CCI 
2017N332005_02	24-SEP-2018	Protocol Amendment 2: The primary motivation for this amendment was to update the eligibility criteria to impose a minimum renal function (as defined by creatinine clearance) in light of the first-in-human data that showed the main route of clearance for GSK3036656 is through the kidneys. As a result of the long half-life of GSK3036656, an updated dosing strategy has also been implemented incorporating the use of loading doses.
2017N332005_03	24-JUL-2019	Protocol Amendment 3: To document the increase in exposure limits and change in eligibility criteria following the availability of new non-clinical data.
TMF-11820616	17-FEB-2021	Protocol Amendment 4: To allow for standard of care medication administered in the study to be either Rifafour e-275 or an equivalent generic alternative and to allow for analysis of the primary endpoint data to be performed on additional cohorts.
TMF-13331420	12-MAY-2021	Protocol Amendment 5: Variability in the rate of change of log 10 CFU observed in the trial to-date is lower than anticipated. Due to this, and slower than anticipated recruitment, the study sample size has been re-calculated. The potential to modify the haemoglobin exclusion and stopping criteria in subsequent cohorts investigating lower doses of GSK3036656 has been added.

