## 2.4. Statistical Analyses

The primary endpoint, EBA CFU0-14, will be analysed using a mixed effects model including treatment, day, BMI and treatment-by-day as covariates. Secondary endpoints of EBA CFU0-2, CFU2-14, TTP0-2, TTP0-14 and TTP2-14 will be analysed similarly to the primary endpoint. See Section 7: Efficacy Analyses for further details.

Plasma concentration-time data will be analysed by non-compartmental methods, the following pharmacokinetic parameters will be determined: Maximum observed plasma drug concentration (Cmax), Time to maximum observed plasma drug concentration (tmax), Area under the concentration-time curve from time of dosing to last quantified concentration, regardless of time (AUC(0-t)), Area under the concentration-time curve from time of dosing extrapolated to 24 hours (AUC(0-24)) and Trough Concentration (Cτ). AUC(0-t) or AUC(0-24) and Cmax may be used for assessment of dose proportionality. Trough concentration (Cτ) samples will be used to assess attainment of steady state. See Section 9 for further details.

Safety data, including AEs, clinical laboratory values, vital signs and ECG, will be summarised descriptively according to GSK's Integrated Data Standards Library (IDSL) standards. See Section 8: Safety Analyses for further details.

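### If the haemoglobin criterion is relaxed for later lower-dose cohorts, the dose-versus-slope reading would mix dose with eligibility, and no planned efficacy analysis separates the two

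*SAP*

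**What the plan says.** **Eligibility.** Protocol 6.2 excludes "haemoglobin <10.0 g/dL; this criterion may be adjusted following DEC review (see Section 11"). Section 11 gives the DEC the power "To adjust the haemoglobin exclusion and stopping criteria if no haematological abnormalities are observed" in Cohort 3, the highest-dose cohort, and then sets the scope: "For the subsequent cohort(s) receiving a lower dose of GSK3036656, the haemoglobin exclusion criterion will be lowered to <8.0 g/dL". The Amendment 5 summary gives the reason: "A high number of screen fails have occurred due to haemoglobin levels being slightly lower than the current exclusion criteria (<10.0 g/dL"), described there as common in this population. No proportion is given.

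**Analysis.** Protocol 10.3.1 specifies a "mixed effects model including treatment, day, BMI and treatment-by-day as covariates", and SAP 2.4 repeats these terms. SAP 7.1.5.1 (Models 1 and 2) and SAP 7.2.5.1 contain no haemoglobin term. The six exploratory covariates in SAP 5.3 begin "Additional covariates of age (continuous), creatinine clearance (continuous), HIV status (yes/no), diabetes status (yes/no), smoking status" and end with baseline cavities. The only Model 1 sensitivity run concerns participants who withdrew early or were replaced. SoC data are pooled across cohorts.

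**Awareness.** The SAP is based on Amendment 5, and its Introduction records the change: "The potential to modify the haemoglobin exclusion and stopping criteria in subsequent cohorts investigating lower doses of GSK3036656 has been added". Its own list of amendments contains no corresponding analysis.

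**Use of the between-dose reading.** Protocol Section 11 and SAP 3.1 say the efficacy analysis during escalation is meant to inform dosing and the dose-response curve. SAP Figure 2.4 plots CFU slope against dose with a regression line, for both the dose-escalation and the final deliverable.

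**The concern.** Dose groups come from sequential cohorts, so randomisation balances GSK3036656 against SoC within a cohort but does not balance one dose against another. Comparing doses relies on the cohorts being similar in other respects. Section 11 allows one documented difference to enter that is tied to dose by design: only cohorts below the Cohort 3 dose, and only after it, could admit participants at 8 to 10 g/dL.

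If such participants clear bacilli at a different rate, part of that difference would appear in Figure 2.4 as an effect of dose. Pooling SoC across the two enrolment regimes also gives up the concurrent control as a within-cohort reference. BMI in Model 1 does not help, because it enters as a main effect and shifts the level of log10 CFU, not its slope.

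**Working it through.** **1. The plan's own figure.** Protocol 10.1.2 states roughly a 90% chance of a negative observed mean with a true change of -0.06, SD 0.15 and n = 9. In closed form, P = Φ(0.06 / (SD/√n)).
- n = 9, SD 0.15: Φ(0.06/0.050) = Φ(1.20) = 88.5%, which agrees.
- Protocol 10.1.1, n = 15, SD 0.2: Φ(0.06/0.0516) = 87.7%. This is a little low, but the Monte Carlo standard error with 1000 runs is about 1 point.

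So -0.06 log10/day is a fair yardstick for what follows.

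**2. Size of a possible bias.** Let f be the share of a relaxed cohort that enters at 8 to 10 g/dL, and δ the difference in their daily slope. Bias in that arm's mean slope relative to the other doses = f × δ. The documents give neither quantity, so both are assumed. SE for nine participants at SD 0.067 (the larger GSK3036656 value in Protocol 10.1.2) = 0.067/√9 = 0.0223.

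| f | δ (log10/day) | Bias | % of 0.06 | In SE units |
|---|---|---|---|---|
| any | 0 | 0 | 0 | 0 |
| 0.10 | 0.01 | 0.001 | 1.7 | 0.04 |
| 0.25 | 0.02 | 0.005 | 8.3 | 0.22 |
| 0.50 | 0.04 | 0.020 | 33 | 0.90 |

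If the bias weakens the slope, the chance of a negative mean (SD 0.15, n = 9) falls from 88.5% to Φ(0.059/0.050) = 88.1% at the low end and Φ(0.040/0.050) = 78.8% at the high end.

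A mid-range example: 4 of 9 participants with δ = 0.02 to 0.04 gives 4/9 × δ = 0.009 to 0.018. With SD 0.06 (assumed, between the observed 0.053 and 0.067), one arm's SE is 0.06/√9 = 0.020. The SE of a difference between 9 and 15 participants is √(0.0036/9 + 0.0036/15) = 0.025. The shift is therefore 0.35 to 0.70 of that SE.

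**3. Which model term would adjust a slope.** A random-intercept mixed model was simulated with no true dose difference, f = 0.5 and δ = 0.03 (expected bias 0.015), in 150 runs. The spurious slope difference between doses was:
- no haemoglobin term: 0.0145/day (Monte Carlo SE 0.0019);
- haemoglobin status as a main effect: 0.0145/day (0.0019);
- haemoglobin status by time: 0.0009/day (0.0023).

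The procedure in SAP 7.1.5.1 adds a covariate, then treatment-by-covariate. Neither contains time, so adding haemoglobin to the SAP 5.3 list under that procedure would leave the slopes unadjusted. The treatment-by-covariate form was reasoned through, not simulated.

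**4. Precision of a restricted run.** If 4 of 9 are dropped, SE = 0.06/√5 = 0.027 instead of 0.020.

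**The case against.** The strongest case against acting is that nothing here is certain. The DEC's power is discretionary and conditional, participants at 8 to 10 g/dL must then enrol, and haemoglobin must be related to kill rate. No passage states that last link, and without it the bias is zero. The Amendment 5 rationale says failing values were only slightly below the limit, which points to participants close to the old criterion. The assumed mid-range shift is smaller than one arm's standard error. The study tests no hypothesis, the primary output is a slope per arm, and sequential cohorts can differ in many ways. All of this stands, and it limits the weight of the point.

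A reader might also infer that low-dose activity in general would be confounded. The documents do not support that. The 5 and 15 mg cohorts already had Day 14 data when the sample size was re-estimated, and Cohort 3 (30 mg as Dose 3 in SAP 5.1) also precedes the change. Only Dose 4 or 5 below the Cohort 3 dose is exposed, and those doses are not yet set, so such a cohort need not be the lowest on the curve.

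Nor would the difference be invisible. Table 3.12 should carry a baseline row for haemoglobin by arm, judging by the programming note on the same template for Table 2.2, and Figure 3.4 plots haematology for each participant by treatment. These displays would show a shift in haemoglobin between arms. They cannot show what it does to the CFU slope, and they do not separate SoC by cohort.

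What survives is narrower: a foreseeable eligibility difference tied to dose, a planned display that reads slope against dose, and no planned efficacy analysis on a common eligibility window.

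**Conclusion.** The point holds in conditional form. If the DEC relaxes the criterion, later lower-dose cohorts and their SoC participants would be enrolled under a different haemoglobin limit from the 5, 15 and 30 mg cohorts, and dose would be partly aliased with eligibility in the dose-escalation efficacy analysis and Figure 2.4. This could bias the between-dose reading by about 0.001 to 0.020 log10 CFU/mL/day, or 1.7% to 33% of 0.06. Those figures rest wholly on assumed shares of 10% to 50% and assumed slope differences of 0.01 to 0.04. The estimated slope of each arm remains valid for the participants it enrolled. The documents do not support saying that the comparison will be confounded, only that the plan has no way to check. This is an inexpensive improvement and not a flaw in the primary analysis. No view is taken on the haemoglobin threshold itself.

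**What to change.** In SAP 7.1.5.1, pre-specify the following, to apply only if the criterion is changed:

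- One Model 1 sensitivity run, with a matching version of Figure 2.4, limited to participants with screening haemoglobin of at least 10.0 g/dL in every cohort and in pooled SoC. Use the screening value, because eligibility is judged on it, whereas the SAP 5.2 baseline is the latest pre-dose value.
- Optionally, and as exploratory only, a model with baseline haemoglobin and a haemoglobin-by-time term. State beside it that overlap is limited: if screening followed the old limit, Cohorts 1 to 3 have almost nobody below 10.0 g/dL, so the adjustment leans on extrapolation.

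The primary model stays as it is. The cost is a short SAP addition and one or two extra runs on data already collected. The downside is precision: on the 4-of-9 example the restricted run loses 44% of the affected arm and its SE rises from about 0.020 to 0.027, so the result should be labelled supportive. Fixing it before the dose-response result is seen keeps the choice independent of that result.
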